### 9.7.6 Sensitivity analyses

- Lack of information on terminations of pregnancy due to foetal anomalies from SWE may yield underestimation of the prevalence of MCA in the study population. In FIN, 10.5% of total cases with MCAs were diagnosed and recorded in TOPFAs between 1993 and 2010. However, this may bias the study results on MCAs if the risk for TOPFA differs between women with different MSDMD exposures or MS exposure in SWE. Separate analyses will be performed on MCAs for the Norwegian and the Finnish data including pregnancy terminations, stillbirths and live births, and another analysis including live births only. The analyses will also be stratified by country as the follow-up times of the newborn babies for recording the malformations in MBRs or Malformation Register may vary between the countries.

- Information on pregnancy terminations is available from GW 12 onwards from the Norwegian data, and therefore, information on early pregnancy terminations conducted before GW 12 could result in incomplete data. Therefore separate analyses by trimesters on pregnancy terminations will be performed.
- In additional sensitivity analyses on MCAs, outcomes will be assessed where exposure occurred prior to pregnancy and through to the end of the first trimester of pregnancy. Also, an analysis of MCA outcomes from live births only will be performed.
- As there is a geographical variation in MS prevalence not only between countries but also within countries, descriptive statistics will be conducted by country and university hospital district level. Country and region will also be included in the multivariate analyses.
- Possible changes in diagnostic criteria and developments in examination and treatment throughout time, as well as trends in obstetric care may influence the estimated prevalence. The study periods also vary between the countries, which may reflect the deviation in the results. Therefore the year of pregnancy outcome will be taken into account in the descriptive statistics and analyses. By taking into account the data from 1 Jan 2005 to 31 Dec 2014 from each country (time period in which the data is available i.e. overlaps for all 3 countries), a separate sensitivity analysis of the primary objective will be provided as well.
- New MS immunomodulatory therapies (e.g. cladribine, mitoxantrone and teriflunomide) can have long-term side effects. The proportion of pregnancies in different study cohorts that are using these treatments with respective treatment duration and duration of unexposed period at LMP will be reported. In addition, two separate sensitivity analyses are to be performed: 1) analysis further adjusting for a variable never vs. ever exposed to cladribine, mitoxantrone or teriflunomide as a covariate and 2) analysis adjusting for the duration of cladribine, mitoxantrone or teriflunomide treatment prior to LMP as a covariate.
- Regarding the identification of cohort 1, exposure to IFN- $\beta$  without exposure to any other MSDMD is based on drug purchase data. It is possible that individuals in this cohort have received other MSDMDs in a hospital. In addition, steroids may be given by infusion in a hospital. To account for this possibility, a sensitivity analysis will be done for primary objective #2 using only those individuals from cohort 1 who are unexposed to the proxy MSDMD/steroid hospital exposure during the pregnancy period. To do this, a proxy for the MSDMD /steroid infusion hospital exposure will be defined for cohort 1, based on diagnoses (ICD-10 codes) and all operations codes (Nomesco classification of surgical procedures (NCSP) based classification) recorded pertaining to any hospital visits during the pregnancy period.
- To investigate if cohort 5 could be a proxy for the severity of disease with impact on the pregnancy outcomes, the descriptive statistics (n, %) will be presented for each pregnancy outcome (i.e. serious pregnancy outcome, elective TOPFA, stillbirth, live birth and MCA) in women with MS exposed to other MSDMDs but not to IFN- $\beta$  or glatiramer acetate (Copaxone®) or dimethyl fumarate (Tecfidera®) before or during pregnancy. The impact of disease severity will be assessed by presenting the prevalence of the outcomes for cohort 5 versus cohort 3.

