**Population:** The target study population consists of Finnish, Swedish and Norwegian women diagnosed with MS who have been pregnant during the study period from 1996 to 2014. The pregnancy may have resulted in an induced abortion, spontaneous abortion, ectopic pregnancy, stillbirth, or live birth during the study period. A pregnancy will be considered unexposed if exposure is stopped at least three months prior to LMP (exceptions: six months for mitoxantrone and cladribine). MSDMDs that will be considered aside from IFN  $\beta$ -1a, IFN  $\beta$ -1b and Peg IFN- $\beta$ -1-a: human normal immunoglobulin (Anatomical Therapeutic Chemical (ATC) code, J06BA02), cyclophosphamide (L01AA01), methotrexate (L01BA01, L04AX03), cladribine (L01BB04), mitoxantrone (L01DB07), alemtuzumab (L01XC04), glatiramer acetate (Copaxone®) (L03AX13), leflunomide (L04AA13), natalizumab (L04AA23), fingolimod (L04AA27), teriflunomide (L04AA31), azathioprine (L04AX01), dimethyl fumarate (N07XX09).

**Comparisons:** The primary comparisons will be performed between the following study cohorts:

- i) women with MS exposed to IFN- $\beta$  (but not to other MSDMDs) (cohort 1) and women with MS unexposed to any MSDMDs (cohort 3), and,
- ii) women with MS exposed to IFN- $\beta$  (but not to other MSDMDs) (cohort 1) and women with MS unexposed to IFN- $\beta$  regardless of exposure to other MSDMDs (cohort 4).

**Outcomes:** The primary outcome variable is a serious adverse pregnancy outcome, which is defined as a composite endpoint including elective TOPFA, MCA, or stillbirth. Other outcome variables include live births, stillbirths, elective TOPFA or elective termination due to other reasons, MCA, spontaneous abortions, ectopic pregnancies, and several other perinatal adverse health outcomes.

**Data sources:** The study database will be constructed from the Nordic health registers: Drugs and pregnancy Project (DPP) (FIN), Patient Registers, MS Registers, Prescription Registers, Medical Birth Registers (MBRs), Malformation Register, Causes of Death Register, and Population Registers.

**Study size:** The estimated number of pregnancies in MS patients is 1671, encompassing data from:

- i) FIN: 1 January 1996 – 31 December 2014;
- ii) SWE: 1 July 2005 – 31 December 2014;
- iii) NOR: 1 January 2004 – 31 December 2014.

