#### 9.2.3 Study period

The study periods in the different countries are as follows: FIN, 1 January 1996 – 31 December 2014; SWE, 1 July 2005 – 31 December 2014; NOR, 1 January 2004 – 31 December 2014. The start of the study period is determined by the availability of exposure data in each country. The end of the study period is determined by the availability of data on malformations. In FIN the follow-up period for the registration of MCA is 12 months after birth, in SWE 6 months. In NOR malformations are registered in the MBR and the newborns are followed until the end of the stay at the birth clinic (usually at least 4 days).

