## 9.5 Study size

Based on the feasibility study (cf. Annex 1) it is estimated that a total of 1671 MS pregnancies would be available for the current study from FIN, SWE and NOR. This total sample size was estimated as follows: In FIN 433 MS pregnancies were observed between 1 January 1996 and 31 December 2010 of which 86 were in 2010. For the actual study, data from FIN from 1 January 2011 to 31 December 2014 will also be used, and therefore the total number of available MS pregnancies was estimated to be 777 (433 + 4\*86, where 86 is the number of MS pregnancies in 2010). In SWE 329 MS pregnancies were observed during the time period 1 July 2005 – 31 December 2011 (329/6.5 years = 51 per year). Because the study period in SWE is from 1 January 2005 to 31 December 2014, the estimated number of MS pregnancies in SWE is 482 (329 + 3\*51). In NOR, 330 MS births were expected to occur in the time period 1 January 2004 – 31 December 2014, which was estimated to be 80% of all MS pregnancies excluding terminations of pregnancies. The number of MS pregnancies available in the study from NOR was thus estimated to be 412 (330/0.8). The total number of 1671 MS pregnancies available for the study is obtained as the sum of these estimated numbers (777 + 482 + 412).

From the 433 MS pregnancies in FIN, 102 (24%) and 331 (76%) were identified as exposed and unexposed to any MSDMD, respectively (in SWE, the proportion of unexposed to any MSDMDs was 77%). Furthermore, of the 433 MS pregnancies in FIN, 95 (22%) and 338 (78%) were identified as exposed and unexposed to IFN- $\beta$  regardless of exposure to other MSDMDs, respectively (personal communication with [name], THL, 15 May 2014). Based on these numbers, it was estimated that 76% (= 331/433) of all MS pregnancies will be unexposed to any MSDMD and 78% (= 338/433) of all MS pregnancies will be unexposed to IFN- $\beta$  (regardless of exposure to other MSDMDs). Based on a systematic review of MSDMD usage (La Mantia et al. 2014), it was estimated that 80% of those identified as exposed to IFN- $\beta$  would not be using other MSDMDs (368\*0.8 = 294). Table 5 presents the study population size by exposure to IFN- $\beta$  based on these assumptions.

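### The sensitivity window meant to be common to all three countries starts on 1 January 2005, six months before the Swedish study period begins

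*Protocol*

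**What the plan says.** Section 9.7.6 notes that study periods differ between the countries and that this may affect the results. It therefore plans a separate sensitivity analysis of the primary objective: "By taking into account the data from 1 Jan 2005 to 31 Dec 2014 from each country". It explains the choice of dates in brackets: "time period in which the data is available i.e. overlaps for all 3 countries".

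Section 9.2.3 defines the study periods as "FIN, 1 January 1996 – 31 December 2014", "SWE, 1 July 2005 – 31 December 2014" and "NOR, 1 January 2004 – 31 December 2014". It adds: "The start of the study period is determined by the availability of exposure data in each country". The abstract gives the same Swedish period ("SWE: 1 July 2005 – 31 December 2014"), and so does Table 5.

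One sentence in section 9.5 differs: "Because the study period in SWE is from 1 January 2005 to 31 December 2014".

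The amendment log in section 5 records an extension of the end of the study period and says nothing about the start dates.

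**The concern.** A window common to three countries cannot start before the latest of the three start dates. By section 9.2.3 that date is the Swedish one, 1 July 2005. Section 9.7.6 starts the window six months earlier and still calls it the overlap.

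This is the only analysis in section 9.7.6 that restricts the primary comparison to shared calendar time. Its value lies in the three countries contributing over the same dates. The protocol fixes the date itself, so the conflict is in the protocol's own text and is not a detail left to the statistical analysis plan. With two places giving January and three giving July, whoever programs the analysis has no single instruction to follow.

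**Working it through.** **1. The common window from the stated study periods (section 9.2.3)**

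- Starts: Finland 1 January 1996, Norway 1 January 2004, Sweden 1 July 2005. The latest is 1 July 2005.
- All three end on 31 December 2014.
- Common window: 1 July 2005 to 31 December 2014 = 9.5 years = 114 months.
- Window in section 9.7.6: 1 January 2005 to 31 December 2014 = 10 years = 120 months.
- Months without Sweden: 120 − 114 = 6, and 6/120 = 5% of the calendar time.

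**2. Which Swedish start the protocol's own count supports (section 9.5)**

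- Inputs: 329 Swedish pregnancies from 1 July 2005 to 31 December 2011, which is 6.5 years.
- Rate: 329/6.5 = 50.6 per year, rounded in the protocol to 51.
- The protocol's figure reproduces: 329 + 3 × 51 = 482. The total also reproduces: 777 + 482 + 412 = 1671.
- Years covered: 6.5 + 3 = 9.5, which is a July start. Check: 9.5 × 50.6 = 481.
- A January start would be 10 years: 10 × 50.6 = 506.

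The January date in section 9.5 therefore disagrees with the calculation beside it, and the 482 agrees with section 9.2.3 and Table 5.

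**3. How many pregnancies fall in the half-year without Sweden**

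The protocol gives no 2005 counts by country, so the rates below are assumptions.

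- Finland, low: the mean for 1996–2009, (433 − 86)/14 = 24.8 per year, or 12.4 per half-year.
- Finland, high: the 2010 count, 86 per year, or 43 per half-year. This is an upper bound: six years at 86 would give 516, more than the 433 observed over all of 1996–2010.
- Norway: a flat 412/11 = 37.5 per year, or 18.7 per half-year.
- Half-year total: 12.4 + 18.7 = 31 (low) to 43 + 18.7 = 62 (high).

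**4. Share of the planned window**

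- Low: Finland 5 × 24.8 + 86 + 4 × 86 = 554; Norway 10 × 37.45 = 375; Sweden 482. Total about 1,410. Share 31/1,410 = 2.2%.
- High: Finland capped at the observed 433 for the years to 2010, so 433 + 4 × 86 = 777; Norway 375; Sweden 482. Total about 1,634. Share 62/1,634 = 3.8%.

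**5. Effect on the minimum detectable relative risk, cohort 1 vs cohort 3**

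Inputs are from section 9.5: 7.3% background prevalence, 80% power, 5% two-sided level. Cohort 1 is taken as total × 95/433 × 0.8 and cohort 3 as total × 331/433. The two-proportion calculation first reproduces the protocol's 1.72 with 294 vs 1,270.

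| Case | Total | Cohort 1 | Cohort 3 | Minimum detectable RR |
|---|---|---|---|---|
| Low, window as written | 1,410 | 248 | 1,078 | 1.79 |
| Low, from 1 July 2005 | 1,379 | 242 | 1,054 | 1.80 |
| High, window as written | 1,634 | 287 | 1,249 | 1.73 |
| High, from 1 July 2005 | 1,572 | 276 | 1,202 | 1.74 |

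The correction moves it by about 0.01.

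**The case against.** The strongest reply is that this is a date slip with little consequence. The window as written still drops Finnish data for 1996–2004 and Norwegian data for 2004, which is nearly all of the non-overlap, and 114 of its 120 months are common. Country and year of pregnancy outcome are already in the base model (section 9.7.3), and descriptive results are stratified by both (section 9.7.4). All of this stands, and it limits the size of the point. It does not remove the contradiction between sections 9.7.6 and 9.2.3.

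A reader might infer two stronger conclusions that the protocol does not support.

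- **That the sensitivity analysis is useless as written.** It would still do most of its job, because 95% of its calendar time is shared.
- **That Swedish pregnancies from January to June 2005 would enter and be wrongly classed as unexposed.** Section 9.2.1 admits only pregnancies with an outcome during the study period, and section 9.2.3 starts that period for Sweden on 1 July 2005, so such pregnancies should not enter. Nor does the protocol give the first day of Swedish exposure data: section 9.3.1.1 dates the Swedish prescription register only to 2005. If the data did begin exactly on 1 July 2005, a July window would not by itself secure the look-back of section 9.4, which reaches six months before the last menstrual period. The misclassification argument is therefore not established and is not part of this point.

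**Conclusion.** The error is certain and its effect is small. Section 9.7.6 sets a window that does not meet its own description, because Sweden contributes nothing in the first 6 of 120 months under the study period in the abstract, section 9.2.3 and Table 5. The single January date in section 9.5 does not rescue the window, since the estimate beside it covers 9.5 years from July.

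About 31 to 62 Finnish and Norwegian pregnancies, 2% to 4% of the window, are affected. That range rests on assumed rates of 25 to 86 per year for Finland and 37.5 per year for Norway. The primary analysis does not change. The correction is still worth making, because this is a fixed analysis rule for the primary objective and it is wrong as written.

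**What to change.** In section 9.7.6, start the common window on 1 July 2005. In section 9.5, change the Swedish start to 1 July 2005 so that it matches section 9.2.3 and Table 5; the 482 and the 1671 stay as they are.

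If the sponsor confirms that Swedish exposure data do begin on 1 January 2005, leave section 9.7.6 and the section 9.5 date alone. Correct the abstract, section 9.2.3, Table 5 and the 482 estimate (about 506 at the stated rate), together with the totals that depend on it.

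The first option costs two dates and, under the assumed rates, about 31 to 62 pregnancies in one sensitivity analysis.

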### **Patient Registers (FIN, SWE, NOR)**

Information on hospitalisations due to MS, spontaneous abortions, and ectopic pregnancies will be obtained from the Patient Registers in this study. The Patient Register includes individual-level inpatient data in FIN SWE and NOR (established: FIN 1969, SWE 1987, NOR 2008). Outpatient visits are available since 1998 in FIN, 2001 in SWE and 2008 in NOR. The registers include data on hospitalisations with information on diagnosis (ICD-10), start and end date of the hospitalisation period, operations and other procedures performed, and identification of the hospital and the hospital district. In addition, outpatient visits in the secondary healthcare units and day surgeries are included the registers. No primary care data are currently available.

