##### Exposure to MSDMDs

The Prescription registers in FIN, SWE and NOR cover the whole population, and completeness and accuracy of the registers on reimbursed medications is high (Furu et al. 2009, Furu 2008, Wettermark 2007). For quality assurance, a number of routine data checks are carried out frequently in these registers to identify possible errors or inconsistencies in registers in FIN, SWE and NOR. In FIN the register on reimbursed medications comprises all purchases of medicines directly reimbursed upon purchase at the pharmacies (e.g. 99% in 2007) (National Agency for Medicines and Social Insurance Institution, 2007).

However, there are some limitations to the data collected on exposure:

- Patient-level data on drug use in hospitals and other institutions such as outpatient clinics are not collected routinely in the Prescription Register in FIN, SWE, or NOR, creating observation gaps (Furu et al. 2009). Some drugs are dispensed only through outpatient clinics (for example, antiretroviral drugs), and some new drug groups including some biological drugs (for example, infliximab) are mainly administered in hospitals, and are therefore not usually included in the prescription databases (Table 3). Nonetheless, in FIN information on patients who have a special reimbursement, for example, intramuscular injection, and who want to be injected by a healthcare professional, is included in the prescription register as the patient buys the medicine from pharmacy (personal communication with [name], SII on Finland Jan 5, 2015). However, infusion medicines are always obtained from the hospital pharmacy, and therefore information is not included in the Prescription Register (see section 9.7.6 Sensitivity analyses).

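### The hospital-infusion proxy for cohort 1 cannot be positive in Norway before 2008, so Norwegian 2004–2007 pregnancies stay in that sensitivity analysis unscreened (Finnish 1996–97: partly screened)

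*Protocol*

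**What the plan says.** Cohort 1 (IFN-β only) is identified from pharmacy purchases. Section 9.3.2.1 concedes the blind spot this leaves: "Patient-level data on drug use in hospitals and other institutions such as outpatient clinics are not collected routinely in the Prescription Register". Section 9.7.6 responds with a sensitivity analysis for primary objective 2, "using only those individuals from cohort 1 who are unexposed to the proxy MSDMD/steroid hospital exposure during the pregnancy period". The proxy is to be defined from ICD-10 diagnoses and NCSP-based procedure codes "recorded pertaining to any hospital visits during the pregnancy period".

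Section 9.7.6 does not name the register that supplies those visits. Section 9.3.1.2 does so in effect: "Information on hospitalisations due to MS, spontaneous abortions, and ectopic pregnancies will be obtained from the Patient Registers in this study". It also describes these registers as holding diagnoses, dates, operations and procedures. It dates inpatient data as "established: FIN 1969, SWE 1987, NOR 2008" and adds: "Outpatient visits are available since 1998 in FIN, 2001 in SWE and 2008 in NOR".

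Section 9.2.3 sets the study periods as "FIN, 1 January 1996 – 31 December 2014" and "NOR, 1 January 2004 – 31 December 2014", with Sweden from 1 July 2005.

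**The concern.** A proxy made of recorded hospital visits can be positive only where visits are recorded. The inclusion rule keeps a pregnancy if it shows no proxy exposure, and nothing in it separates a pregnancy that was observed and negative from one that could not be observed. Where the register does not yet exist, absence of data therefore reads as absence of exposure.

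The treatments the proxy is meant to catch were in use during the gap. Table 3 marks intravenous immunoglobulin, mitoxantrone and natalizumab as given only in hospital, with Norwegian authorisation dates of 9 October 1996, 1 August 1988 and 27 June 2006. Section 9.7.6 adds steroid infusions. Avonex and Rebif were authorised in Norway in 2002 and 2003, so cohort 1 pregnancies can arise there from 2004.

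What is at stake is how far this check can be trusted. If the restricted estimate is close to the main one, part of that closeness may come from pregnancies the screen could not touch.

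**Working it through.** **1. Register coverage against study period (sections 9.2.3 and 9.3.1.2)**

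| Country | Study start | Inpatient data from | Outpatient data from | Years affected |
|---|---|---|---|---|
| Finland | 1996 | 1969 | 1998 | 1996–97, outpatient visits only |
| Sweden | July 2005 | 1987 | 2001 | none |
| Norway | 2004 | 2008 | 2008 | 2004–2007, all visits |

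Norway lacks hospital data for 4 of 11 study years (36%). Finland lacks outpatient data for 2 of 19.

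**2. The plan's own figure.** Section 9.5 gives a minimum detectable RR of 1.72 for cohort 1 (294) against cohort 3 (1270) at 7.3% background prevalence, 80% power and 5% two-sided. Solving the pooled-variance two-proportion power formula, the form used by `bpower`, gives 1.717, or 1.720 with 24/331 as the baseline. The figure reproduces.

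**3. Size of the gap in cohort 1.** Section 9.5 expects 412 pregnancies in Norway, 777 in Finland and 1671 in all. The cohort 1 share is 294/1671 = 0.176, assumed equal across countries and years.

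- Norway, even spread: 412 × 4/11 = 150 pregnancies; 150 × 0.176 = 26; 26/294 = 9%.
- Norway, with 25% or 30% of pregnancies before 2008 (assumption): 412 × 0.25 × 0.176 = 18; 412 × 0.30 × 0.176 = 22. Counting only the 330 expected births gives a similar number, 330 × 4/11 × 0.176 = 21. That is a reasonable alternative, because Norwegian spontaneous abortions and ectopic pregnancies come from the same Patient Register and so are also unseen before 2008.
- Finland, even spread: 777 × 2/19 = 82; 82 × 0.176 = 14.
- Finland, geometric growth fitted to 433 pregnancies in 1996–2010 with 86 in 2010: about 10 in the first two years; 10 × 0.176 = 2.
- Together, with Norway evenly spread: 26 + 2 = 28 to 26 + 14 = 40 or 41 before rounding the parts, that is 10–14% of 294.

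**4. How many would be wrongly kept.** Only pregnancies that would have been proxy-positive matter. The protocol gives no rate. If 10–20% had hospital exposure (assumption), then among the 26 Norwegian pregnancies that is 26 × 0.10 = 3 to 26 × 0.20 = 5.

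**5. Power after restriction, cohort 1 against cohort 3**

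| Dropped from cohort 1 | Cohort 1 left | RR, cohort 3 uncut | RR, cohort 3 cut in proportion |
|---|---|---|---|
| Norway 2004–2007 (26) | 268 | 1.75 | 1.75 |
| plus Finland, low (2) | 266 | 1.75 | 1.76 |
| plus Finland, high (14) | 253 | 1.76 | 1.78 |

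These rows count by calendar year of outcome. Pregnancies that began before a start date and ended after it would also go. At about 280 days, with even spread, that is 72.5 × (280/365)/11 = 5 in Norway and at most 777 × 0.176 × (280/365)/19 = 6 in Finland. In the highest case about 51 of 294 (17%) are lost and the RR is about 1.80 with cohort 3 cut in proportion.

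**The case against.** The strongest reply is that the proxy is still to be defined. Section 9.7.6 gives the type of code but no code list and no named register, and section 9.7 defers detail to a separate analysis plan. No sentence tells the analyst to class an uncovered pregnancy as unexposed, and one could read unexposed to the proxy as presupposing that it can be observed. A reader might infer that the protocol instructs otherwise. It does not: retention is a consequence of the rule, not a stated instruction. The point still stands, because the protocol has already fixed both the data (hospital-visit codes) and the retention rule, and on its own dates the two do not work together for Norway before 2008.

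Other sources might help. The Norwegian MS Register (from 1998) holds disease-modifying treatment and co-medication, and the birth registers hold some maternal diagnoses and interventions. The protocol assigns neither to the proxy, so this shows a possible remedy rather than a safeguard in place.

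Three provisions might seem to cover the gap. The missing-data category in section 9.7.7 is not linked to this restriction, and an absent visit does not appear as a missing value. The wording about available time periods in sections 9.4 and 9.7.1 concerns confounders and effect modifiers. The 2005–2014 common-window analysis still contains Norway 2005–2007.

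It is tempting to say that Finnish 1996–97 pregnancies are also unscreened. They are not, since Finnish inpatient records go back to 1969. The Finnish count may also sit near its low end: only Betaferon, and Avonex from March 1997, were authorised there in those two years. Likewise Betaferon reached Norway only in September 2006 and natalizumab in June 2006, so early exposure there may be lower than an even spread implies.

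**Conclusion.** The point holds, as a minor one. Under the rule as written, about 26 of 294 cohort 1 pregnancies (9%), or about 18–22 if fewer fall in the early years, are Norwegian pregnancies from 2004–2007 that cannot be proxy-positive. A further 2–14 Finnish pregnancies are screened on inpatient visits only. Sweden has no gap.

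These counts rest on the protocol's planned totals, on one cohort 1 share applied to every country and year, on the stated assumptions about spread over time, and on the Patient Registers being the source of the visits.

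A reader might go further and infer that the primary result is biased, or that agreement between the restricted and main estimates would be an artefact. The documents support neither. The primary analysis does not use the proxy, about nine-tenths of cohort 1 is screened at least in part, and the number wrongly kept may be only a handful. What can be said is that the check removes less hospital exposure than it sets out to, by an amount its output would not reveal.

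**What to change.** State in section 9.7.6, or in the analysis plan, that this sensitivity analysis includes only pregnancies whose whole pregnancy period lies within hospital-register coverage: Norway from 1 January 2008, and Finland from 1 January 1998 so that outpatient visits are covered. Apply the same calendar window to cohorts 3 and 4; otherwise cohort 1 and its comparators would span different years. Report by country how many cohort 1 pregnancies were not assessable, separately from those found proxy-positive, and name the register that supplies the visits.

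The cost is a paragraph of text and a smaller sample in one sensitivity analysis: roughly 10–14% of cohort 1, with the minimum detectable RR against cohort 3 rising from 1.72 to about 1.75–1.78, and a little more once straddling pregnancies are excluded. Earlier Norwegian years are lost to this check unless another source is formally assigned to the proxy. The primary analysis needs no change.
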